9. Has HIV or nonstable hypothyroidism, diabetes, cardiovascular disease, or respiratory disease or has another chronic medical condition that is not considered to be adequately treated in the opinion of the investigator.

Note: The prescribed doses and regimens of prior medications should be stable for ≥ 3 months before Visit 1 (Screening) and there should not be expected changes for these medications before and during the study. Treatment with a medication is considered stable if dose adjustments reflect optimizing treatment rather than reacting to significant changes in the treated conditions. Timing for substitution of prohibited medications is presented in Table 2.

- 10. Has a severe, acute or chronic medical or psychiatric condition or laboratory abnormality that may increase the risk associated with study participation or administration of study intervention or may interfere with the interpretation of study results and, in the opinion of the investigator or Sponsor, would make the participant inappropriate for entry into this study.
- 11. Is at imminent risk of self-harm, based on clinical interview and responses on the C-SSRS, or of harm to others in the opinion of the investigator. Participants must be excluded if they report suicidal ideation with intent, with or without a plan or method (eg, positive response to item 4 or 5 in assessment of suicidal ideation on the C-SSRS) in the *past 2 months* or suicidal behavior in the *past 6 months*.

PROTOCOL/AMENDMENT NO.: 006-03

Prior/Concomitant Therapy

- 12. Does not meet the requirements defined in Section 8.1.7.2 (Concomitant Medications, Table 2) that specify when prohibited medications/products or prohibited doses for allowed medications must be stopped relative to Visit 1 (Screening).
- 13. Failed to adequately respond in the investigator's or qualified delegate's clinical judgment to treatment with ketamine or esketamine for the current or a prior episode of MDD.
- 14. Previously received electroconvulsive therapy (within the past 10 years), deep brain stimulation, or vagal nerve stimulation for treatment of depression. TMS is not exclusionary unless received within 6 weeks before Visit 1 (Screening).

Prior/Concurrent Clinical Study Experience

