Note 2: If the investigator identifies a clear cause for the liver enzyme elevations unrelated to study intervention, then study intervention may be continued with approval by the Sponsor.

- The participant meets either of the following criteria for QTcF interval at a visit (**Note**: ECGs will be performed in triplicate [Section 8.3.4]):
 - The average of the 3 QTcF intervals based on either the local ECG printout or subsequent central vendor overread is >500 msec.
 - The average of the 3 QTcF intervals based on either the local ECG printout or subsequent central vendor overread increased by >60 msec, relative to the central vendor overread average at Visit 4 (Day 1).
- The participant reports suicidal ideation with intent, with or without a plan or method through an AE or C-SSRS (ie, a positive response to Items 4 or 5 in the assessment of suicidal ideation on the C-SSRS) or suicidal behavior. If the reported suicidal ideation is passive, and participant expressly denies any intent to act, and who, after evaluation, is not judged to be at serious risk for self-harm during the study, the participant may continue on study intervention. Refer to Sections 8.3.7.1 on Clinical Assessments for Suicidal Ideation and Behavior Monitoring (for requirements pertaining to the evaluation of such events), and Section 8.4.7 for Events of Clinical Interest.
- The participant is unable to tolerate treatment with study intervention before Visit 6 (Week 2).

Note: Participants who are unable to tolerate study intervention after a dose modification to the intended regimen should be discontinued from study intervention.

The participant begins to use a prohibited medication/therapy/product or a prohibited dose of an allowed medication listed in Section 8.1.7.2 (Concomitant Medications, Table 2). This criterion includes participants who test positive (local or central) for a drug of abuse (except cannabis, which is not prohibited if abuse or substance use disorder is ruled out).

Note: Participants who are willing and able to safely (per the investigator) stop using the prohibited medication/therapy/product (including drugs of abuse) or reduce from a prohibited to an acceptable dose for an allowed medication through Visit 9 (Post-dose Follow-up Visit) may continue study intervention at the investigator's discretion.

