9.4.2 Safety Endpoints

Safety and tolerability will be assessed by clinical review of all relevant parameters including AEs, laboratory values, ECGs, and vital signs.

Responses on the C-SSRS are classified according to 11 prespecified categories (Ideation: Passive, Active-nonspecific, Active-method, Active-method and intent, and Active-method, intent and plan; Behavior: Preparatory actions or behaviors, Aborted attempt, Interrupted attempt, Suicide attempt, and Completed suicide; Non-suicidal Self-Injurious Behavior). The most severe treatment-emergent event within each of 3 broad categories (suicidal ideation, suicidal behavior, and non-suicidal self-injurious behavior) reported at a visit will be used for analysis and reporting. An event is considered treatment-emergent during the assessment phase if it is either newly emerged or is more severe than the most severe event reported to have occurred in the study-defined pretreatment reference period.

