Dizziness AEs of moderate or severe intensity and gait disturbance independent of feelings of dizziness AEs are Tier 2 AEs.

Tier 3 Events

Safety endpoints that are not Tier 2 events are considered Tier 3 events. Only point estimates by treatment group are provided for Tier 3 safety parameters.

Categorical Safety Measures

C-SSRS

The percentage of participants with any treatment-emergent suicidal ideation or with any treatment-emergent suicidal behavior will be analyzed per the tiered analysis strategy outlined above, and will be considered as either Tier 2 or Tier 3 events, depending on the number of participants with an event observed within each treatment group. Additionally, the 11 prespecified categories of suicidal ideation and behavior will be summarized. Participant counts (and cumulative counts) for each category will be based upon the most severe treatment-emergent event observed during the assessment period.

In constructing the treatment-emergent C-SSRS analyses, a pretreatment reference period is required, from which a baseline score for each of the 3 categories (ideation, behavior, nonsuicidal self-injury) is derived. For this study, the baseline score for each of the 3 categories will be taken as the maximum score arising from the 3 predose C-SSRS administrations. The first predose administration references lifetime history. Each subsequent predose administration references the timeframe since the last predose administration.

It is noted that the first predose administration actually consists of 2 separate administrations; 1 using lifetime as the reference period and another using fixed-time intervals (6 months for behavior and 2 months for ideation). The fixed-time administration is solely included for inclusion/exclusion purposes (noting that the contemporaneous maximum lifetime baseline score may not be less than the maximum fixed-time baseline score by definition).

Continuous Safety Measures

For continuous measures such as changes from baseline in laboratory, vital signs, and ECG parameters, summary statistics for baseline, on-treatment, and change from baseline values will be provided by treatment group in table format.

Table 7 summarizes the safety analysis.

Table 7 Analysis Strategy for Safety Parameters

Safety Tier	Safety Endpoint	p-value	95% CI for Treatment Comparison	Descriptive Statistics
Tier 2	Any AE		X	X
	Any Serious AE		X	X
	Any Drug-related AE		X	X
	Any Serious and Drug-related AE		X	X

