9.6.4 Summaries of Baseline Characteristics, Demographics, and Other Analyses

The comparability of the treatment groups for each relevant demographic and baseline characteristic will be assessed by the use of tables and/or graphs. No statistical hypothesis tests will be performed on these characteristics.

The number and percentage of participants screened and randomized and the primary reasons for screening failure and discontinuation will be displayed. Demographic variables, baseline characteristics, primary and secondary diagnoses, and prior and concomitant therapies will be summarized by treatment either by descriptive statistics or categorical tables.

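### Both planned C-SSRS summaries count only events that go beyond lifetime history, so an on-study recurrence at a level already in a participant's history enters no specified C-SSRS table

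*Combined protocol and SAP*

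**What the plan says.** Section 9.6.2 plans two C-SSRS summaries. One is the percentage of participants with any treatment-emergent suicidal ideation or any treatment-emergent suicidal behavior, handled under the safety tiers. The other covers the 11 categories: "Participant counts (and cumulative counts) for each category will be based upon the most severe treatment-emergent event observed during the assessment period". Section 9.4.2 applies the same filter to what goes forward for reporting: "The most severe treatment-emergent event within each of 3 broad categories".

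Under Section 9.4.2 an event is treatment-emergent if "it is either newly emerged or is more severe than the most severe event reported to have occurred in the study-defined pretreatment reference period". Section 9.6.2 takes the baseline in each of the three domains (ideation, behavior, non-suicidal self-injury) as "the maximum score arising from the 3 predose C-SSRS administrations. The first predose administration references lifetime history". A recent-window administration also exists (2 months for ideation, 6 months for behavior), but it plays no part in the analysis: "The fixed-time administration is solely included for inclusion/exclusion purposes".

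Table 7 has no C-SSRS row, and neither Section 9.4.2 nor Section 9.6.2 specifies a C-SSRS summary without the treatment-emergent filter.

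**The concern.** Measured against a lifetime maximum, the participants with the most severe past suicidality have the least room to register an event. Such participants can be enrolled. Exclusion 11 in Section 5.2 says "Participants must be excluded if they report suicidal ideation with intent, with or without a plan or method", but its window is 2 months for that ideation and 6 months for behavior. Older events do not exclude unless the investigator judges imminent risk.

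Section 2.2.2 states that there are no safety data for this drug in treatment-resistant depression, and the C-SSRS is the trial's prospective suicidality instrument. As planned, its tables show what was new or worse than a participant's whole history. They do not show what occurred on treatment, by category and arm. For laboratory values, vital signs and ECGs, by contrast, Section 9.6.2 plans baseline, on-treatment and change-from-baseline summaries.

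**Working it through.** The plan gives no figure to reproduce here, so the check applies its counting rule, looks for other outputs that would show the omitted events, and sizes the effect of one omission.

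**1. The rule applied to ideation.** Number the five ideation categories of Section 9.4.2 from 1 (passive) to 5 (active with method, intent and plan), with 0 for none. Let L be the lifetime maximum. Reading new emergence as going beyond the baseline, an on-study level counts only if it exceeds L.

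| Lifetime maximum L | On-study levels counted | On-study levels not counted |
|---|---|---|
| 0 | 1 to 5 | none |
| 1 | 2 to 5 | 1 |
| 2 | 3 to 5 | 1, 2 |
| 3 | 4, 5 | 1 to 3 |
| 4 | 5 | 1 to 4 |
| 5 | none | 1 to 5 |

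An equal-level recurrence never counts. New emergence is not defined separately. On a looser reading, a milder category never reported before could count. The equal-level case does not depend on that choice, because a level already in the history is neither new nor more severe.

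**2. The other two domains.** If behavior severity follows the order listed in Section 9.4.2, a repeat suicide attempt does not exceed a lifetime attempt. Non-suicidal self-injury is a single category, so a participant with any lifetime occurrence cannot exceed baseline.

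**3. Other outputs.**
- Section 7.1 requires discontinuation of study intervention when "The participant reports suicidal ideation with intent, with or without a plan or method through an AE or C-SSRS", or for suicidal behavior, with an exception for ideation evaluated as passive.
- Section 9.6.4 then provides that "The number and percentage of participants screened and randomized and the primary reasons for screening failure and discontinuation will be displayed".
- AE, SAE and ECI reporting (Section 8.4) has no lifetime filter. Appendix 3 makes an exacerbation of a pre-existing condition an AE, and Section 8.4.6 exempts no disease-related event.
- The ECI listing in Section 8.4.7 covers suicidality only when it has been reported as an AE. Appendix 3 also keeps expected fluctuations without worsening out of the AE definition.

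Ideation with intent and suicidal behavior should therefore surface somewhere, though not by C-SSRS category and arm. What may be absent from all outputs is mainly ideation without intent, or non-suicidal self-injury, that nobody reports as an AE.

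**4. Weight of one omitted participant.** With the planned arm sizes (Section 9.9.1: 56 daily, 28 intermittent, 56 placebo) as denominators, the gap between the unfiltered and planned percentages is k/n for k omitted participants.

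| Omitted participants, k | n = 28 | n = 56 |
|---|---|---|
| 1 | 1/28 = 3.6 points | 1/56 = 1.8 points |
| 2 | 2/28 = 7.1 points | 2/56 = 3.6 points |
| 3 | 3/28 = 10.7 points | 3/56 = 5.4 points |

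The range k = 1 to 3 is an assumption; the documents give no basis for the true number.

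**5. Data available.** The Schedule of Activities has the C-SSRS at Visits 1 and 4 before the first dose, and at Visits 5, 6, 7, 8, 9 and 10 after it: six administrations, plus the Down-titration Visit if one occurs. An unfiltered table needs no new assessment.

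An editorial point only: Section 9.6.2 speaks of three predose administrations, while the Schedule shows two visits. The count may include both parts of the first administration. The baseline maximum is the same either way.

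**The case against.** The strongest reply is that the lifetime reference is a deliberate and consistent choice. Sections 9.4.2 and 9.6.2 agree, the role of the recent-window administration is explained, and treatment-emergent incidence is a legitimate quantity. Participants outside its definition are not undercounted; a different quantity is being asked for. That is right, and it is why the lifetime-referenced analysis should stay.

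Second, ideation that was absent at entry and returns would usually meet the AE definition and become an ECI, intent-level events trigger discontinuation, and the siDMC reviews accruing unblinded safety data. This stands in part and confines the possible complete omission mainly to lower-level events. But none of these routes is a planned output by C-SSRS category and arm, and the AE route depends on someone reporting the event as an AE.

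Third, the number affected is unknown, and the percentage points above are simply the weight of one participant. That is true. They show how much one omission matters in arms this small, not how many to expect.

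Fourth, a table regardless of history mixes persistence with recurrence. It does, and this has to be stated beside it.

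Finally, the sSAP is not available and might contain such a table. Section 9 uses the sSAP for changes to non-confirmatory analyses, but a table that is not specified in the available documents cannot be assumed.

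**Conclusion.** The concern holds. Under the stated rules, an on-study event at a level already in a participant's lifetime history is counted in neither planned C-SSRS summary, and no other C-SSRS table is specified. A milder event is also left out on the natural reading of the definition.

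This is a gap in tabulation, not in participant monitoring, and it implies no bias in the drug-placebo comparison: if omitted recurrences are balanced across arms, the risk difference is unchanged. For an assumed 1 to 3 omitted participants in an arm, the planned percentage lies 3.6 to 10.7 points (n = 28) or 1.8 to 5.4 points (n = 56) below the unfiltered one. The point should be addressed, because the C-SSRS tables cannot otherwise show on-treatment suicidality in the participants with the most history. The conclusion about the rule rests on the text alone; only the size rests on an assumption.

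**What to change.** Keep the lifetime-referenced analysis and add one descriptive table by arm: the number and percentage of participants in each of the 11 C-SSRS categories, based on the most severe event after the first dose, whatever the history. Show two periods separately:

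- **On-treatment:** post-first-dose administrations through the EOT/DC Visit, including any Down-titration or unscheduled administration.
- **Follow-up:** later visits, which for completers are Visits 9 and 10.

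Using the EOT/DC Visit as the boundary keeps the off-treatment visits of early discontinuers out of the on-treatment column. The wording can go into the sSAP before unblinding.

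The cost is one table from data already collected, with no new assessment and no change to any hypothesis test. The drawback is that it will also show persistence or recurrence of pre-existing symptoms, so it must be presented and read beside the lifetime-referenced table.

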9.6.3 Statistical Methods for Pharmacokinetic Analysis

Plasma concentrations will be summarized by nominal timepoint using the following (non-model-based) descriptive statistics: N (number of participants with non-missing data), arithmetic mean, standard deviation, arithmetic percent CV (calculated as $100 \times \text{standard}$ deviation/arithmetic mean), median, minimum, maximum, GM, and geometric percent CV (calculated as $100 \times \text{sqrt} (\exp(s^2)$ -1), where s^2 is the observed variance on the natural log-scale). The effect of genetic polymorphism of CYP2C19 on MK-1942 PK may be assessed and described in a separate document.

9.6.4 Summaries of Baseline Characteristics, Demographics, and Other Analyses

The comparability of the treatment groups for each relevant demographic and baseline characteristic will be assessed by the use of tables and/or graphs. No statistical hypothesis tests will be performed on these characteristics.

The number and percentage of participants screened and randomized and the primary reasons for screening failure and discontinuation will be displayed. Demographic variables, baseline characteristics, primary and secondary diagnoses, and prior and concomitant therapies will be summarized by treatment either by descriptive statistics or categorical tables.

9.7 Interim Analyses

One non-binding interim futility analysis will be performed in this study. The interim analysis will be performed when the first ~60% of randomized participants either complete Week 3 or discontinue before Week 3. The interim analysis calculation assumes the same SDs used for the study power and sample size estimates, and assumes that the remaining data (after interim analysis) will be distributed similarly to that observed at the interim. The endpoints, timing, and purpose of the interim analysis are summarized in Table 8 below.

Key Endpoints for Interim Analysis	Timing of Interim Analysis	Purpose of Interim Analysis			
Change from baseline at Week 3 in MADRS total score (MK-1942 daily dose versus placebo) Change from baseline at Week 1 in MADRS total score (MK-1942 intermittent dose versus placebo)	First ~60% of randomized participants either complete Week 3 or discontinue prior to Week 3	Assess futility			
MADRS=Montgomery-Asberg Depression Rating Scale					

Table 8 Summary of Interim Analysis Strategy

Study enrollment is likely to be ongoing at the time of the interim analysis. Blinding to treatment assignment will be maintained at all investigational sites. The results of the interim analysis will not be shared with the investigators prior to the completion of the study. Participant-level unblinding will be restricted to an internal unblinded statistician and

PROTOCOL/AMENDMENT NO.: 006-03

statistical programmer performing the interim analysis, who will have no other responsibilities associated with the study.

Treatment-level results and/or participant-level data from the interim analysis will be provided by the unblinded statistician to the siDMC which consists of Sponsor personnel (and external experts, as appropriate). Limited additional Sponsor personnel may be unblinded to the treatment level results of the interim analysis, if required, in order to act on the recommendations of the siDMC. The extent to which individuals are unblinded with respect to results of the interim analysis will be documented by the unblinded statistician.

The processes by which recommendations and decisions are reached and communicated are documented in the siDMC charter for the Sponsor. The protocol-specific siDMC charter will be referenced in the CSR. Prior to final study unblinding, individuals who have been unblinded at any level will not be involved in any discussions regarding modifications to the protocol, statistical methods, identification of protocol deviations, or data validation efforts after the interim analyses.

If the study is stopped early, the CSR will include all available data up to and including the close-out visits. This approach to include all available information is in line with the ICH-E9 guideline, the ITT principle and the CHMP guideline on adaptive designs.

The decision of whether to terminate the study for futility will be based on CP, ie, the likelihood of correctly detecting a (standardized) treatment difference at the end of the study given the results at the interim, corresponding to the primary hypotheses (ie, MADRS change from baseline at Week 3 (MK-1942 daily dose versus placebo) and at Week 1 (MK-1942 intermittent dose versus placebo). If the CP is <10% for both primary hypotheses, the study may be stopped for futility. If the truth is a SES of 0.230 for MK-1942 daily dose versus placebo and 0.277 for MK-1942 intermittent dose versus placebo (ie, not only do we observe it at the interim, but the remaining data also have that distribution), this equates to a CP of 10% for each contrast. The interim analysis will include data for participants who completed the study or dropped out as well as the partial data of ongoing participants. Additional details regarding the calculation of the CP will be described in the sSAP.

The operating characteristics of the interim futility analysis are in Table 9. Based on this information and assuming a correlation of 0.5 between treatment comparisons, the probability the study may be deemed futile if both alternative hypotheses are true is 2.5% based on the marginal probabilities (7.6% and 8.6%). The probability the study may be deemed futile if both null hypotheses are true is 70.7% based on the marginal probabilities (81.3% and 81.4%).

PRODUCT: MK-1942

PROTOCOL/AMENDMENT NO.: 006-03

Table 9 Operating Characteristics of the Interim Futility Analysis

		Daily Dose Group			Inte	Intermittent Dose Group		Probability Study Futile	
Timing of Futility Interim Analysis	Futility CP Criterion	Futility SES Boundary	Probability Futile Based on SES=0	Probability Futile Based on SES=0.6	Futility SES Boundary	Probability Futile Based on SES=0	Probability Futile Based on SES=0.7	Both Null Hypotheses True	Both Alternative Hypotheses True
First ~60% randomized who complete or discontinue before Week 3	<10%	0.230	81.3%	7.6%	0.277	81.4%	8.6%	70.7%	2.5%
CP=conditional power, SES=standardized effect size									

PROTOCOL/AMENDMENT NO.: 006-03

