Sample Size and Power	The planned sample size is 140 (56 in the MK-1942 daily dose group, 28 in the MK-1942 intermittent dose group, and 56 in the placebo group). There is ~92% probability that at least 1 of the 2 MK-1942 groups will be superior to placebo as measured by change in MADRS total score at Week 3 (MK-1942 daily dose versus placebo) or Week 1 (MK-1942 intermittent dose versus placebo) under the primary assumptions as provided in Table 10.			

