model including calculated change from baseline at Week 1, Week 2, Week 3, and Week 4. The model will handle missing data (both intermittent missing and monotone missing due to dropout) using the missing at random assumption. This model will be used to generate confidence intervals and p-values (compared with placebo). This model assumes a different mean for each treatment at each of the repeated time points in the analysis. In this model, time is treated as a categorical variable so that no restriction is imposed on the trajectory of the means over time. The analysis model will include categorical terms for treatment, number of treatment failures (1; >1) for the current episode of moderate-to-severe MDD, and week, as well as a continuous term for baseline response. In addition, the model will also include the interaction terms of week-by-treatment and week-by-baseline response. The treatment difference in terms of the mean change from baseline at a given time point will be estimated, and as appropriate, tested from the model. An unstructured covariance matrix will be used to model the correlation among repeated measurements. The Kenward-Roger approximation will be used to compute the degrees of freedom [Kenward, M. G. and Roger, J. H. 1997]. A sensitivity analysis will be performed for the primary and key secondary hypotheses to assess the robustness of the primary findings with respect to the handling of missing data. Specifically, a control-based mean imputation approach, with a tipping-point component, will be applied [Mehrotra, D. V., et al 2017]. Details related to this sensitivity analysis will be provided in the sSAP.

As outlined in Table 6, supportive analyses will be performed for the primary and the key secondary hypotheses to assess the robustness of the primary findings with respect to (1) the impact of intercurrent events; and (2) the handling of missing data. Details related to supportive analyses will be provided in the sSAP.

Basic summary statistics will be computed for all efficacy endpoints over time. This minimally includes means and standard deviations for continuous-type endpoints and counts and percentages for categorical endpoints.

Table 6 summarizes the key efficacy analyses.

PROTOCOL/AMENDMENT NO.: 006-03

Table 6 Analysis of Key Efficacy Variables

Endpoint/Variable (Description, Time Point)	Primary vs. Supportive Approach ^a	Statistical Method ^b	Analysis Population	Missing Data Approach	
Primary Hypotheses					

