9.9 Sample Size and Power Calculations

9.9.1 Sample Size and Power for Efficacy Analyses

Sample size was determined based on change from baseline in MADRS total score at Week 3 (for MK-1942 daily dose versus placebo) and Week 1 (for MK-1942 intermittent dose versus placebo). This study will randomize 56 participants into the MK-1942 daily dose group, 28 into the MK-1942 intermittent dose group, and 56 into the placebo group. With these sample

Confidential

sizes and assuming an 8% dropout rate after 1 week and 10% dropout rate after 3 weeks, each treatment comparison has at least 80% (marginal) power to demonstrate superiority compared to placebo at the 2-sided 5% α-level; the probability that at least 1 MK-1942 dosing regimen demonstrates superiority compared with placebo is 92%. These calculations assume the underlying SES for change from baseline in MADRS total score at Week 3 (MK-1942 daily dose versus placebo) is -0.6 (eg, corresponds to a mean treatment difference of -6 points and a standard deviation of 10.0 points) and the underlying SES for change from baseline in MADRS total score at Week 1 (MK-1942 intermittent dose versus placebo) is -0.7 (eg, corresponds to a mean treatment difference of -6.5 points and a standard deviation of 9.3 points) and use a normal test. The intermittent dose group has a smaller sample size due to the anticipation that rapid effect will be seen. Therefore, the primary timepoint of interest is Week 1. Because of the shorter time frame, the sample size has been adjusted to account for lower variance, larger treatment difference, and smaller dropout rate versus the daily dose group, where given the 2 week titration, the primary timepoint of interest is Week 3. The underlying treatment SESs are regarded as a clinically relevant for the difference between the 2 treatments. The sample size calculation also accounts for the interim futility analysis. The SESs for this study were based on results of prior publications for MDD and TRD [Sanacora, G., et al 2014] [Canuso, C. M., et al 2018].

Table 10 provides the assumptions for mean differences, standard deviations, and SESs as well as the marginal power for each treatment comparison, and the probability that at least 1 MK-1942 dosing regimen is successful.

Table 10 Primary Assumptions, Marginal Power, and Probabilities for MADRS Total Score

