Assumed Week 3/Week 1 Mean Treatment Difference in CFB (Daily Dose, Intermittent Dose)	Assumed Week 3/Week 1 CFB SD (Daily Dose, Intermittent Dose)	Assumed Week 3/Week 1 SES (Daily Dose, Intermittent Dose)	Marginal Power for Daily Dose Versus Placebo	Marginal Power for Intermittent Dose Versus Placebo	P (At Least One Hypothesis is Positive, corr.=.5)
(6.0, 6.5)	(10.0, 9.3)	(0.60, 0.70)	83.0%	80.8%	92.0%

CFB=change from baseline; corr=correlation; MADRS=Montgomery-Asberg Depression Rating Scale; SD=standard deviation; SES=standardized effect size

Sample sizes are 56 participants in the MK-1942 daily dose group, 56 participants in the placebo group, and 28 participants in the MK-1942 intermittent dose group.

Assumes dropout rate is 8% at Week 1 and 10% at Week 3.

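### The joint power and futility probabilities use a correlation of 0.5 between the two comparisons, but with equal variances the 56:28:56 design with different read-out weeks cannot exceed 0.408

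*Combined protocol and SAP*

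**What the plan says.** Three joint probabilities depend on how strongly the daily-versus-placebo and intermittent-versus-placebo comparisons are correlated.

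- **Section 9.7 and Table 9, both alternatives true:** "assuming a correlation of 0.5 between treatment comparisons, the probability the study may be deemed futile if both alternative hypotheses are true is 2.5"%, from marginals of 7.6% and 8.6%.
- **Section 9.7 and Table 9, both nulls true:** "The probability the study may be deemed futile if both null hypotheses are true is 70.7"%, from marginals of 81.3% and 81.4%.
- **Section 9.9.1 and Table 10:** "the probability that at least 1 MK-1942 dosing regimen demonstrates superiority compared with placebo is 92"%, from marginal powers of 83.0% and 80.8%. The table column is headed "P (At Least One Hypothesis is Positive, corr.=.5"). Section 9.1 repeats the figure: "There is ~92% probability that at least 1 of the 2 MK-1942 groups will be superior to placebo".

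The plan does not derive the 0.5 and gives no sensitivity range. It does fix most of what determines the correlation. The Table 10 footnote gives 56 participants on the daily dose, "56 participants in the placebo group, and 28 participants in the MK-1942 intermittent dose group". Both regimens are compared with that one placebo arm, the daily regimen at Week 3 and the intermittent regimen at Week 1. Section 9.9.1 uses one SD per comparison; for the daily dose it assumes "a mean treatment difference of -6 points and a standard deviation of 10.0 points", and for the intermittent dose a difference of -6.5 with an SD of 9.3. Section 9.7 carries the same SDs into the interim calculation.

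**The concern.** The correlation between two contrasts with a common control is not a free planning choice. It follows from the arm sizes, the variances and, where the contrasts are read at different visits, the within-participant correlation between those visits. Under equal variances, 0.5 is the value for equal arms read at the same visit. This trial has a half-size intermittent arm and two read-out weeks, and both features lower the correlation.

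At stake is whether the published operating characteristics describe this design. A correlation that is too high understates the chance that at least one comparison succeeds. It also overstates the chance that both fall below the futility boundary, whether the drug works or not.

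**Working it through.** **Inputs from the plan.** Arm sizes 56, 28 and 56; dropout 8% at Week 1 and 10% at Week 3; marginal powers 83.0% and 80.8% (Table 10); marginal futility probabilities 81.3% and 81.4% under the nulls, 7.6% and 8.6% under the alternatives (Table 9).

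**Assumptions.** Equal variance across arms at each week, which is how I read the single SD per comparison. Rho, the within-participant correlation of the change scores at Weeks 1 and 3, is not in the documents; I show 1, 0.75 and 0.5.

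**Step 1: reproduce the plan's figures at r = 0.5.** Let Phi2(a, b; r) be the bivariate normal distribution function and z(p) the normal quantile.

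- At-least-one power = 1 - Phi2(z(0.170), z(0.192); 0.5) = 92.48% (stated 92.0%)
- Stop, both nulls true = Phi2(z(0.813), z(0.814); 0.5) = 70.58% (stated 70.7%)
- Stop, both alternatives true = Phi2(z(0.076), z(0.086); 0.5) = 2.40% (stated 2.5%)

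The two futility figures reproduce to within 0.1 point. The power figure differs by about 0.5 point. To match the printed values exactly, r would have to be 0.54, 0.51 and 0.52 respectively.

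**Step 2: the correlation the design gives.** Only placebo participants contribute to both contrasts, and the SDs cancel:

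r = rho x (1/56) / sqrt[(1/56 + 1/56)(1/28 + 1/56)] = rho / sqrt(2 x 3) = 0.408 x rho

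With dropout, the placebo arm has 56 x 0.92 = 51.52 participants at Week 1 and 56 x 0.90 = 50.4 at Week 3. If the second set is contained in the first, the constant becomes 0.408 x sqrt(50.4/51.52) = 0.404. Since rho cannot exceed 1, the ceiling is about 0.41.

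**Step 3: joint probabilities at the design's correlation, printed marginals.**

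| rho | r | At least one positive | Stop, both nulls true | Stop, both alternatives true |
|---|---|---|---|---|
| plan's input | 0.500 | 92.48% | 70.58% | 2.40% |
| 1 | 0.408 | 93.40% | 69.63% | 1.97% |
| 0.75 | 0.306 | 94.34% | 68.66% | 1.56% |
| 0.5 | 0.204 | 95.20% | 67.77% | 1.21% |

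By the same method throughout, the correlation alone moves power up by 0.92 to 2.72 points. It moves the both-nulls stopping probability down by 0.95 to 2.81 points and the both-alternatives one down by 0.43 to 1.19 points.

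**Step 4: could unequal SDs give 0.5?** Let k be the placebo SD divided by a common active-arm SD. Then r = rho x k^2 / sqrt[(1 + k^2)(2 + k^2)]. This equals 0.5 at k = 1.21 if rho = 1, at k = 1.35 if rho = 0.9 and at k = 1.72 if rho = 0.75. For large k it tends to rho, so at rho = 0.5 no ratio reaches 0.5. The plan states no difference in SDs between arms.

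**The case against.** **The 0.5 is a disclosed assumption, and the futility figures follow from it.** True: this is an unsuitable input rather than a slip in calculation. But the input is largely fixed by the stated allocation, and with equal variances it lies outside what that allocation permits.

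**Equal variance is inferred.** Section 9.9.1 offers its SDs as examples. Section 9.6.1 says "An unstructured covariance matrix will be used to model the correlation among repeated measurements", but that describes the analysis model, and it does not say whether the matrix is common to all arms. This stands as a condition on the 0.408. It does not support 0.5, which would need a larger placebo SD that the plan nowhere mentions.

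**Rho is unknown, so the replacement figures are illustrative.** This stands. Only the ceiling is derived; at rho = 0.3, for example, power would be 95.9%. The direction is the same for every rho.

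**The printed marginals may not match the stopping rule.** Section 9.7 permits stopping only if conditional power is below 10% for both comparisons, whereas the printed 83.0% and 80.8% are close to what per-comparison stopping gives (83.2% and 80.4%). Simulating the both-comparisons rule gives at-least-one power of 92.9% at r = 0.5 and 93.8% at r = 0.408. The level moves by about 0.4 point, but the shift due to correlation is again about 0.9 point. So the figures in the table above are not final values.

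**The interim includes partial data.** More participants may contribute Week 1 than Week 3 data. If the Week 3 participants are a subset and each arm has the same proportions, simple means bring in a factor sqrt(n at Week 3 / n at Week 1), which is below 1. That lowers the correlation further.

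**Conclusion.** The point holds. Given equal variance across arms, the correlation is 0.408 x rho (0.404 x rho with the stated dropout), so 0.5 is not attainable and all three joint probabilities rest on an input the design does not have. For rho between an assumed 0.5 and 1, the correlation shifts at-least-one power by about 1 to 3 points, the both-nulls stopping probability by about 1 to 3 points, and the both-alternatives one by about 0.4 to 1.2 points.

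This is minor. Understated power and overstated false stopping are conservative errors. The overstated chance of stopping when neither regimen works is the one optimistic error, at a non-binding look. Sample size, marginal powers, tests, alpha and the 10% conditional-power criterion do not depend on this correlation. The remaining gap of about 0.5 point between 92.5% and the stated 92.0% is not explained by it.

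**What to change.** In section 9.7 and the Table 10 heading, replace 0.5 with the correlation implied by the allocation. State the equal-variance assumption and the value or range of rho used, and say whether the dropout-adjusted constant is applied. Recalculate the three joint probabilities from the sponsor's own unrounded marginals, checking that these reflect the both-comparisons stopping rule, and carry the results through sections 9.1, 9.7 and 9.9.1 and Tables 9 and 10. As a guide, the printed marginals with rho from 0.5 to 1 give 93.4 to 95.2% for at-least-one power, 67.8 to 69.6% for stopping under both nulls and 1.2 to 2.0% for stopping under both alternatives. If the sponsor prefers to keep 0.5, it should state the unequal SDs and the rho that produce it.

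The cost is SAP text and three probabilities wherever they appear. The only unwelcome result is that the stated chance of stopping when both nulls are true falls by about 1 to 3 points.
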